#### 2.1. Study Objectives

## 2.1.1. Primary Objectives

 To determine the effectiveness of PCV13 to prevent hospitalised VT- pneumococcal CAP among adults aged ≥60 years in Madrid using a TND, overall and among immunocompetent persons only.

#### 2.1.2. Secondary Objectives

- To describe the distribution of SP serotypes using blood, high-quality respiratory cultures, and a serotype-specific UAD assay among adults 60 years of age and older with CAP.
- To determine the proportion of persons with respiratory pneumococcal carriage among adults 60 years of age and older presenting with CAP by testing saliva specimens using both conventional culture and the sensitive molecular method of polymerase chain reaction (PCR) for the detection of two target genes (lytA and piaB).
- To describe the proportion of participants with CAP and with S. pneumoniae (SP+CAP)
  who present with underlying at-risk and high-risk medical conditions.

DMB02-GSOP-RF02 5.0 Statistical Analysis Plan Template 05-Dec-2019
PFIZER CONFIDENTIAL
Page 7
TMF Doc ID: 98.03

 To describe the frequency and type of antibiotic resistance among SP isolates, overall and by specimen type.

## 2.1.3. Exploratory Objectives

- To estimate incidence rates for hospitalised CAP and SP+CAP (both overall and radiologically confirmed) in the surveillance region within the limitations of the expected under ascertainment of hospital-based screening process and current diagnostic testing.
- To compare the effectiveness of PPV23 to that of PCV13 in preventing cases of hospitalised VT- pneumococcal CAP among adults aged ≥60 years using a test-negative study design, overall and among immunocompetent persons only.
- To compare pneumococcal serotype results from high-quality respiratory specimens (standard-of-care), UAD1/2 (study procedure), and saliva specimens taken for carriage testing (study procedure).
- To estimate incidence rates for hospitalised CAP among adults aged ≥60 years with underlying at-risk and high-risk medical conditions, in aggregate and for individual risk conditions within the limitations of the expected under ascertainment of hospital-based screening process and current diagnostic testing.

## 2.1.4. Additional COVID-19 Exploratory Objectives

- To determine if the frequency of pneumococcal infection differs between hospitalised CAP patients with COVID-19 infection compared to those without COVID-19 infection, overall and stratified by age, sex, and pneumococcal risk status.
- Among the subset of hospitalised CAP patients with COVID-19 identified, to determine if
  the proportion who experience severe clinical outcomes (eg, intensive care unit [ICU] stay,
  mechanical ventilation, prolonged hospitalisation, and sequelae) differs between those
  with pneumococcal co-infection compared to those without pneumococcal co-infection,
  overall and stratified by age, sex, and pneumococcal risk status.
- Using a TND to determine the VE of PCV13 against severe COVID-19 clinical outcomes among COVID-19 positive hospitalised CAP patients, overall and among immunocompetent persons only.
- To assess if frequency of pneumococcal carriage differs for those with current or past COVID-19 infection, overall and stratified by age, sex, and pneumococcal risk status.

## 2.1.5. Additional 2022 RSV Exploratory Objectives

 To determine the proportion of persons with RSV infection among adults 60 years of age and older presenting with CAP by testing saliva specimens using the PCR method.

DMB02-GSOP-RF02 5.0 Statistical Analysis Plan Template 05-Dec-2019
PFIZER CONFIDENTIAL
Page 8
TMF Doc ID: 98.03

#### 2.2. Study Design

This study is a low interventional, prospective, multicentre, hospital-based study involving adults 60 years of age and older hospitalised with CAP at participating sites. Hospital surveillance data will be used for incidence rates calculations. Vaccine effectiveness will be calculated using a TND. The approximate study duration will be 4 years.

Assuming 15% PCV13 vaccination coverage among controls, 60% VE, 9% VT serotype prevalence, a ratio of 1:10 case and controls and with alpha=0.025 and 80% power, enrolment of 170 cases and 1,692 controls would be required to allow appropriate evaluation of the study objective.

#### 2.2.1 Population

This study will prospectively enroll adults, aged 60 years and over, who are hospitalised with CAP in one of the study hospitals.

#### 2.2.2. Variables

The screening log will collect demographic data, including eligibility of the participants for the study, whether consented, and confirmation of diagnosis by chest rediology. If consent is given then further data would be collected including: medical and vaccination history, smoking and alcohol use as well as details of current illness including all symptoms, treatment, severity score, vital signs and test results. At follow up visits confirmation of CAP or alternative diagnosis, event disposition and vital status will be recorded at 30 and 180 days.

#### 2.2.3. Data sources

In this study, the sources of data will include both CRF and non-CRF. The CRF data include hospital records, including radiology and laboratory results, as well as primary care medical records. The non-CRF sources will be the Screening Log, reference lab, and local sources. Local sources will provide the data on the count of population living in the surveillance area, overall, by age group, and with the risk condition(s). The database named SISPAL maintained by the Regional Health System will be used to obtain vaccination histories.

#### 3. ENDPOINTS AND BASELINE VARIABLES: DEFINITIONS AND CONVENTIONS

#### 3.1. Primary Endpoint

 VE will be calculated as 1 minus the OR comparing the odds of having received PCV13 for cases and controls, multiplied by 100%, overall and restricted to immunocompetent subjects only.

## Cases and Controls for VE against PCV13

The cases are the patients with CAP (i.e., enrolled population who have a final diagnosis consistent with CAP) and in whom PCV13 serotypes are identified by any method including UADs, routine culture of blood, pleural fluid, or other high-quality respiratory tract specimen. PCV13 serotypes are as follows: 1, 3, 4, 5, 6A, 6B, 7F, 9V, 14, 18C, 19A,

DMB02-GSOP-RF02 5.0 Statistical Analysis Plan Template 05-Dec-2019 PFIZER CONFIDENTIAL Page 9 TMF Doc ID: 98.03 19F and 23F. Only sputum isolates from high-quality specimens (Appendix 4) will be considered in assigning case status. Participants with VT serotype who also have a Non-Vaccine Type (NVT) serotype will also be classified as cases.

The following criteria must be met to be a control:

- hospitalized patient with CAP
- met the inclusion/exclusion criteria, and
- PCV13 or related serotype (e.g., 6C) are not identified from any sources

A second model will be developed excluding immunocompromised persons (Appendix 2.4) to evaluate PCV13 VE without those who may not be able to respond to the vaccine.

## Cases and Controls for VE against PPV23

The cases are the patients with CAP in whom any one of the 23 serotypes in PPV23: 1, 2, 3, 4, 5, 6B, 7F, 8, 9N, 9V, 10A, 11A, 12F, 14, 15B, 17F, 18C, 19A, 19F, 20, 22F, 23F, and 33F is identified (including those where a NVT serotype is also identified).

The following criteria must be met to be a control for PPV23:

- hospitalized patient with CAP,
- met the inclusion/exclusion criteria, and
- PPV23 are not identified from any source

#### 3.2. Secondary Endpoint(s)

 Proportion of CAP events for each pneumococcal serotype, PCV-13, and 20-valent pneumococcal conjugate vaccine (PCV20) serotypes among all CAP subjects with UAD1/2 testing (overall) and among all CAP subjects with a pneumococcus identified.

The denominators for this endpoint are:

- all CAP patients having their UAD 1 or 2 results available,
- all CAP patients with a pneumococcus identified (Sp+) from UAD, Binax, blood culture, or high-quality respiratory cultures

Note: If a participant, for example, is positive for a PCV20 serotype (e.g., 8) and a non-PCV20 serotype (e.g., 17F), the participant will be counted as PCV20 Sp+ and not non-PCV20 Sp+.

 Proportion of CAP events where the pneumococcus was identified from saliva by culture or PCR divided by all CAP events where the subject had a valid saliva specimen test result.

DMB02-GSOP-RF02 5.0 Statistical Analysis Plan Template 05-Dec-2019
PFIZER CONFIDENTIAL
Page 10
TMF Doc ID: 98.03

The denominator will be the CAP population with valid saliva specimen test result.

- Proportion of CAP subjects with underlying at-risk and high-risk medical conditions, overall and restricted to those with pneumococcus isolated from blood, high-quality respiratory cultures, and a serotype-specific urinary antigen detection (UAD) assay.
  - For overall, the denominator will be all CAP population. For participants restricted to pneumococcus, the denominator will be the CAP population in whom a pneumococcus is identified from culture, UAD, or Binax.
- Proportion of S. pneumoniae isolates with antibiotic resistance identified by standard of care testing, overall and by resistance type.

The analysis will be conducted among participants who are Sp+ by culture among the CAP population for whom the data on antibiotic resistance are available. If the antibiotic resistance information is missing or not done for a participant, then the participant will be excluded from the analysis. For participants whose Sp isolates were shipped to the Reference Lab, antibiotic resistance results will be used in the analysis. Participants who are detected as Sp+ via culture method but without serotype information ('Not Serotyped') will also be included in the analysis.

Antibiotic resistance will be reported in the eCRF as one of the following categories:

- SUSCEPTIBLE
- RESISTANT
- NOT APPLICABLE
- o UNKNOWN

The following antimicrobials will be considered: Penicillin, Amoxicillin, Cefotaxime, Erythromycin, Clindamycin, Tetracycline, and Levofloxacin.

Antibiotic susceptibility profile will be reported in the analysis as follows:

Report in the	Reported in the eCRF
analysis	
Susceptible	Susceptible
Resistant	Resistant
Multidrug resistant	Resistance to penicillin and resistance to two classes of non-\u00b3-lactam antibiotics (i.e. two of the following: Erythromycin, Levofloxacin, Tetracycline)

#### 3.3. Other Endpoints

#### 3.3.1. Exploratory Endpoints

 Number of CAP events identified by screening log divided by number of persons ≥60 years in surveillance region.

DMB02-GSOP-RF02 5.0 Statistical Analysis Plan Template 05-Dec-2019
PFIZER CONFIDENTIAL
Page 11
TMF Doc ID: 98.03

The denominator will be the number of individuals aged ≥60 years living in the hospitals' catchment area. The data on the denominator will be obtained from INE (National Statistical Institute).

 Final adjusted VE point estimate for PPV23 subtracted from final adjusted VE subtracted for PCV13, overall and among immunocompetent persons only.

#### Cases and controls for VE against PCV13

The cases are the patients with CAP in whom PCV13 serotypes are identified by any method including UADs, routine culture of blood, pleural fluid, or other high-quality respiratory tract specimen. PCV13 VTs are as follows: 1, 3, 4, 5, 6A, 6B, 7F, 9V, 14, 18C, 19A, 19F and 23F. Only sputum isolates from high-quality specimens (Appendix 4) will be considered in assigning case status. Participants with VT serotype who have also an NVT serotype will also be classified as cases.

The controls are the patients with CAP without a VT serotype (including the CAP events for which the pneumococcus was not identified or pneumococcus was present but the serotype was unknown) that met the inclusion and exclusion criteria. These will serve as test-negative controls. Participants with 6C serotype identified (VT serotype) will be excluded from the controls.

The definition of the immunocompromised persons is given in Appendix 2.4.

## Cases and controls for VE against PPV23

The cases are the patients with CAP in whom any one of the 23 serotypes in PPV23: 1, 2, 3, 4, 5, 6B, 7F, 8, 9N, 9V, 10A, 11A, 12F, 14, 15B, 17F, 18C, 19A, 19F, 20, 22F, 23F, and 33F is identified.

The controls are the patients with NVT episode of CAP. Participants having both VT and NVT serotypes will not be included in the controls.

 Percent agreement in serotype results between specimen types for events that have both types available (Three comparisons: 1. high-quality respiratory culture [standard-of-care specimen] versus UAD1/2; 2. UAD1/2 versus saliva carriage sample; 3. High-quality respiratory culture versus saliva carriage sample).

This analysis will include the participants who have at least two of the following with a valid test result: high quality respiratory culture, UAD1/2, or saliva samples.

• Number of CAP events identified by screening log multiplied by the proportion of CAP subjects with specific risk condition(s) divided by the estimated number of persons ≥60 years residents in the hospitals' catchement area with the same specific risk condition(s), in aggregate for at-risk and high-risk conditions and for individual risk groups if the size of risk group is adequate for a stable estimate.

DMB02-GSOP-RF02 5.0 Statistical Analysis Plan Template 05-Dec-2019
PFIZER CONFIDENTIAL
Page 12
TMF Doc ID: 98.03

The denominator will be the population living in the hospitals' catchment area with the risk condition(s), which will be obtained from local source(s) depending on availability.

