12.1.1. Defining Cases and Test-negative Controls

For the analysis of the primary endpoint, we will define cases as events involving hospitalised for CAP in whom PCV13 serotypes are identified by any method including UAD1 or routine culture of blood, pleural fluid, or other high-quality respiratory tract specimen. PCV13 VT serotypes are as follows: 1, 3, 4, 5, 6A, 6B, 7F, 9V, 14, 18C, 19A, 19F and 23F. Only sputum isolates from high-quality specimens (see Section 11.1) will be considered in assigning case status. All other episodes of CAP that met the inclusion criteria for the study, but for whom PCV13 or related serotypes are not identified from any source (ie, non-vaccine type [NVT] only) will serve as test-negative controls. Subjects with vaccine-related serotypes (eg, 6C) will be excluded from controls for the primary analysis. Subjects with VT serotype who also have an NVT or vaccine-related serotypes will be classified as cases. Subjects may only contribute one CAP event to any given VE analysis.

For PPV23 VE, cases will be those with one of 23 serotypes in PPV23: 1, 2, 3, 4, 5, 6B, 7F, 8, 9N, 9V, 10A, 11A, 12F, 14, 15B, 17F, 18C, 19A, 19F, 20, 22F, 23F, and 33F (including those where a NVT or vaccine-related serotype is also identified). Events with vaccine-related serotypes (either alone or in combination with an NVT) will be excluded from the controls for the primary analysis. Controls will be those with only nonvaccine serotypes (ie,

all other serotypes). Subjects with VT serotype who also have an NVT or vaccine-related serotypes will be classified as cases.

In sensitivity analyses, we will estimate PCV13 and PPV23 VE using different control group. In this case, controls will be defined as non-VT pneumococcal CAP (Broome method).¹³ That is, controls will be patients in whom pneumococcus is detected by blood/pleural/high-quality sputum culture, *BinaxNOW*[®], or UAD1/2 positive; but VT or vaccine-related serotypes are not identified from culture or UAD1/2. (ie, serotypes identified are not VT or related serotypes). In the second sensitivity analysis, we will define controls as CAP patients in whom pneumococcus was not detected by any method (culture, UAD, or *BinaxNOW*[®]), similar to a recently published TND.¹⁴

If PCV20 use is initiated in the surveillance area during the study, PCV20 vaccinated persons would be excluded from both case and control groups for the PCV13 VE analysis.

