#### Serotype at group level

Vaccine type (VT): If any of the serotypes covered in the 20-valent pneumococcal conjugate vaccine (PCV20), 13-valent pneumococcal conjugate vaccine (PCV13), the 7-valent pneumococcal conjugate vaccine (PCV7) or the 23-valent pneumococcal polysaccharide vaccine (PPV23) are detected either by UAD or culture.

PCV20: If any of the following serotypes 1, 3, 4, 5, 6A, 6B, 7F, 8, 9V, 10A, 11A, 12F, 14, 15B, 18C, 19A, 19F, 22F, 23F, and 33F are detected either by UAD or culture.

PCV13: If any of the following serotypes 1, 3, 4, 5, 6A, 6B, 7F, 9V, 14, 18C, 19A, 19F, and 23F are detected either by UAD or culture

cPCV7 (complimentary seven serotype): If any of the following serotypes 8, 10A, 11A, 12F, 15B, 22F, and 33F are detected by UAD or culture

PCV7: If any of the following serotypes 4, 6B, 9V, 14, 18C, 19F and 23F are detected by UAD or culture

PPV23: if any of the folling serotype 1, 2, 3, 4, 5, 6B, 7F, 8, 9N, 9V, 10A, 11A, 12F, 14, 15B, 17F, 18C, 19F, 19A, 20, 22F, 23F and 33F detected by UAD or culture.

DMB02-GSOP-RF02 5.0 Statistical Analysis Plan Template 05-Dec-2019
PFIZER CONFIDENTIAL
Page 30
TMF Doc ID: 98.03

Non-vaccine type (NVT): If none of the serotypes covered in PCV20, PCV13, PCV7, or PPV23 are detected from both UAD and culture.

Non-typeable (NT): A cultured isolate that could not be serotyped. This is a valid result and so will be summarized as a separate line. Note that this is not the same as a missing serotype result.

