## 6.3.2.1. Exploratory Endpoint 2 - Main Analysis

In this analysis, the VE of PCV13 against VT (PCV13) pneumococcal CAP will be obtained from the primary analysis as described in Section 6.1.1.1. The same method will be used to estimate the VE of PPV23 against VT (PPV23) pneumococcal CAP. The crude difference will then be calculated as:

VE of PCV13 against VT (PCV13) pneumococcal CAP – VE of PPV23 against VT (PPV23) pneumococcal CAP

To evaluate the differences of the effectiveness of these two vaccines, the ORs from both the models that used conditional logistic regression using the propensity matching cases and controls, will be tested using the likelihood ratio and/or z-score test as described in Appendix 3.4.

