# **Appendix 2. Data Derivation Details**

# Appendix 2.1. Serotypes

Central laboratories will perform pneumococcal serotyping for all participants with *S. pneumoniae* (*Sp*) isolated by culture.

VT is defined as serotypes included in PCV20, PCV13, PCV7 or the PPV23

PCV7 serotypes: 4, 6B, 9V, 14, 18C, 19F and 23F.

DMB02-GSOP-RF02 5.0 Statistical Analysis Plan Template 05-Dec-2019
PFIZER CONFIDENTIAL
Page 47
TMF Doc ID: 98.03

PCV13 serotypes: 1, 3, 4, 5, 6A, 6B, 7F, 9V, 14, 18C, 19A, 19F, and 23F.

PCV20 serotypes: 1, 3, 4, 5, 6A, 6B, 7F, 8, 9V, 10A, 11A, 12F, 14, 15B, 18C, 19A, 19F, 22F, 23F, and 33F.

PPV23 serotypes: 1, 2, 3, 4, 5, 6B, 7F, 8, 9N, 9V, 10A, 11A, 12F, 14, 15B, 17F, 18C, 19F, 19A, 20, 22F, 23F and 33F.

[figure not shown]
NVT are serotypes that are not included in any of PCV20, PCV13, PCV7, or PPV23.

Non-typeable or Untypeable (UT) is defined as a result which could not be serotyped. This is a valid result and so will be summarized as a separate line. Note that this is not the same as a missing serotype result.

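### The SAP defines PPV23 controls in two ways that do not agree, and neither repeats the protocol's exclusion of vaccine-related serotypes

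*SAP*

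**What the plan says.** SAP 3.1 requires of a PPV23 control only hospitalised CAP, the entry criteria, and that "PPV23 are not identified from any source". CAP with no pneumococcus found qualifies.

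SAP 3.3.1 says of the same vaccine: "The controls are the patients with NVT episode of CAP". It adds: "Participants having both VT and NVT serotypes will not be included in the controls". The PCV13 paragraph just above it defines controls as CAP without a vaccine type, "including the CAP events for which the pneumococcus was not identified or pneumococcus was present but the serotype was unknown", and removes 6C. The PPV23 paragraph has neither provision.

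The SAP gives NVT two meanings. Section 5.4, which classifies results at group level, applies it "If none of the serotypes covered in PCV20, PCV13, PCV7, or PPV23 are detected from both UAD and culture". Appendix 2.1 defines it as a property of a serotype: "NVT are serotypes that are not included in any of PCV20, PCV13, PCV7, or PPV23".

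Protocol 12.1.1 says of PPV23: "Events with vaccine-related serotypes (either alone or in combination with an NVT) will be excluded from the controls for the primary analysis". It then describes PPV23 controls as having nonvaccine serotypes only.

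SAP 6.3.2.1 takes PCV13 VE from the primary analysis and continues: "The same method will be used to estimate the VE of PPV23 against VT (PPV23) pneumococcal CAP". It does not name the PPV23 control set.

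**The concern.** An analyst cannot derive the PPV23 control variable without choosing between SAP 3.1 and SAP 3.3.1, and within 3.3.1 between two meanings of NVT. Nothing in the SAP settles the choice, so it could be made after the data are seen. It determines the PPV23 odds ratio, the difference in VE and its z-test. SAP 6.1.1.2 also plans sensitivity analyses against PPV23 types, so the ambiguity reaches beyond one endpoint.

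The lost exclusion is a separate matter. The protocol keeps vaccine-related types out of the PPV23 controls, presumably because a vaccine might act on them too. The SAP keeps that rule for PCV13 and omits it for PPV23, and its version history gives no reason.

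**Working it through.** **1. What the plan sizes.** SAP 2.2 gives 170 cases and 1,692 controls for PCV13. Inputs are control exposure 0.15, OR 0.40, two-sided alpha 0.025, power 80% and ratio 1,692/170 = 9.95. Case exposure is 0.15 × 0.40 / (0.85 + 0.15 × 0.40) = 0.0659. The Fleiss formula with continuity correction returns 170 and 1,692 (157 cases without the correction). The evaluable total is 1,862. No size is given for PPV23 VE or for the comparison.

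**2. Serotype sets (SAP 3.4, 5.4, Appendix 2.1).** UAD-1 covers 13 types and UAD-2 covers 11, so 24 in all. Twenty-three are the PPV23 types; the remaining one is 6A, which is in PCV13 and PCV20. Every UAD type is therefore a vaccine type. Binax gives no serotype. Only a cultured isolate can show a non-vaccine serotype.

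**3. Who is a PPV23 control, by sole finding.**

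| Finding | SAP 3.1 | SAP 3.3.1, NVT per 5.4 | SAP 3.3.1, NVT per App. 2.1 |
|---|---|---|---|
| No pneumococcus | control | control | not a control |
| Pneumococcus, serotype unknown | control | control | not a control |
| 6A | control | not a control | not a control |
| 6C (culture) | control | control | control |
| Other non-vaccine type (culture) | control | control | control |

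The two definitions disagree on either meaning of NVT. On the 5.4 meaning they differ by 6A-only patients. On the Appendix 2.1 meaning they differ by nearly the whole test-negative group. A cultured 6C patient is a control throughout, whereas the protocol excludes vaccine-related types. 6C is the only related type the documents name, and they name it in the PCV13 context.

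**4. How few culture-only controls (assumption).** Protocol 7 gives IPD at age 60 and over for 2013-2015: 17.09 per 100,000 overall, 1.25 for PCV7 types and 3.45 for the other PCV13 types. It gives 25% for serotypes 8 and 22F together.
- Non-vaccine share, at most: 1 − (1.25 + 3.45)/17.09 − 0.25 = 0.475.
- Low culture yield: 17.09/1,577.37 = 1.1% of CAP. High yield: 1,647/22,487 = 7.3% (code 481, Protocol Table 4).
- Controls per 1,862: 1,862 × 0.0108 × 0.475 ≈ 10, up to 1,862 × 0.0732 × 0.475 ≈ 65.

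These proxies are weak. IPD omits sputum culture, code 481 may include antigen-only diagnoses, and the PCV7-type rates (1.25 against 2.07, a 40% fall) do not match the 61% fall stated beside them.

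**5. Effect on precision (illustration).** Assume 300 PPV23-type cases, leaving 1,862 − 300 = 1,562 test-negative controls. SE is the square root of the summed reciprocal cells (SAP Appendix 3.4). Two coverage levels are shown:
- 46.7% in controls: Protocol Table 2, weighted by cohort over ages 60 to 75, with VE 30% assumed.
- 83% in controls and 75% in cases (OR 0.61): age groups weighted by the Table 4 cases, 0.062 × 19.2% + 0.195 × 59.7% + 0.744 × 94.9%.

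| Controls | SE at 46.7% | 95% CI for VE 30% | SE at 83% |
|---|---|---|---|
| 1,562 | 0.129 | 10% to 46% | 0.149 |
| 65 | 0.276 | −20% to 59% | 0.356 |
| 10 | 0.645 | −148% to 80% | 0.852 |

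On the log-OR scale the interval is about 2.1 to 5.0 times wider at 46.7% and 2.4 to 5.7 times wider at 83%. The PCV13 SE at planning values is 0.316. At 46.7% coverage, the ratio of the two odds ratios needed for p<0.05 is exp(1.96 × √(0.316² + 0.129²)) = 1.95 with 1,562 controls. It is 2.28 with 65 and 4.09 with 10.

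**The case against.** The strongest reply is that 3.3.1 was meant to be test-negative. It speaks of an NVT episode, which suits the result-level wording of SAP 5.4 better than the serotype-level wording of Appendix 2.1. Protocol 12.1.1 itself glosses the PCV13 test-negative controls as NVT only. Where the SAP wants pneumococcus-positive controls, in the fourth sensitivity analysis (indirect cohort method), it says so. SAP 6.3.2.1 refers to the primary method, and 6.1.1.1 admits controls whose serotype was not identified.

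Much of this stands. A reader might infer that the plan will compare PCV13 with PPV23 using a handful of culture-only controls; the documents allow that outcome but do not prescribe it. The reply does not remove the conflict, though. The second sentence of the 3.3.1 PPV23 paragraph treats NVT as an identified serotype, the paragraph lacks the inclusive words given to PCV13 just above, and Protocol 12.1.1 restricts PPV23 controls to nonvaccine serotypes. Even on the favourable reading, 6A-only patients are controls in one section and not in the other.

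The objection that the size is assumed also stands. No document gives the culture yield or the PPV23 case count. Protocol Table 2 stops at age 75 and has no time window, whereas SAP 6.1.1.1 counts vaccination 10 or more years ago as unexposed, so 83% may well be too high.

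A reader might also infer that comparing the vaccines on different serotype mixes is an error, since 11 PPV23 types are absent from PCV13. SAP 6.3.2 prespecifies each VE against that vaccine's own serotypes. That is a choice of estimand, not a mistake.

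**Conclusion.** The point holds as an inconsistency within the SAP and a departure from the protocol. The two PPV23 control definitions differ by 6A-only patients at the least, and by almost the whole test-negative group at the most. The protocol's exclusion of vaccine-related serotypes is missing from both. These conclusions follow from the text and the serotype lists alone.

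The loss of precision is conditional. It arises only if Appendix 2.1 governs NVT in 3.3.1, and the figures of 10 to 65 controls and a 2- to 6-fold wider interval rest on the stated assumptions. The effect of the missing exclusion cannot be sized, because the documents give no frequency for 6C or other related types; it is probably small. The documents do not call 6A a PPV23-related type, so its handling has to be decided, not inferred.

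The comparison is exploratory. The primary PCV13 estimate uses its own control definition and is unaffected.

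**What to change.** State one PPV23 control definition in SAP 3.1 and 3.3.1, parallel to the PCV13 one, and cite it in 6.3.2.1: CAP patients who meet the inclusion and exclusion criteria and have no PPV23 serotype and no PPV23-related serotype from any source, with CAP in which no pneumococcus was identified expressly included. List the related serotypes (6C at least) and state how 6A-only patients are handled. Align the sentence in Protocol 12.1.1 that limits PPV23 controls to nonvaccine serotypes, since the 3.3.1 wording appears to come from it.

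Keep the prespecified difference in VE against each vaccine's own serotypes. A comparison limited to the 12 shared serotypes (1, 3, 4, 5, 6B, 7F, 9V, 14, 18C, 19A, 19F, 23F) could be added as an optional sensitivity analysis; it would have fewer PPV23 cases.

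The cost is wording in three SAP sections, one derived variable and one aligned protocol sentence. No new data are needed. The change should be made before PPV23 case and control status is linked to vaccination.
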